### ANCILLARY REVIEWS

| Which ancillary reviews do I need and when do I need them?
Refer to HRP-309 for more information about these ancillary reviews. |   |   |  |
|---|---|---|--|
| Select yes or no  | Does your study...  | If yes...   | Impact on IRB Review   |
|  Yes
 No  | Include Gillette resources, staff or locations  | Gillette Scientific review and Gillette Research Administration approval is required. Contact: [contact]  | Required prior to IRB submission                                       |
|  Yes
 No  | Involve Epic, or Fairview patients, staff, locations, or resources?   | The Fairview ancillary review will be assigned to your study by IRB staff
Contact: [contact]  | Approval must be received prior to IRB committee/designated review.    |
|  Yes
 No  | Include evaluation of drugs, devices, biologics, tobacco, or dietary supplements or data subject to FDA inspection? | The regulatory ancillary review will be assigned to your study by IRB staff
Contact: [contact]

See: https://policy.umn.edu/research/indide | Consider seeking approval prior to IRB submission.                     |
|  Yes
 No  | Require Scientific Review? Not sure? See guidance on next page.   | Documentation of scientific merit must be provided.
Contact: [contact]  |  |
|  Yes
 No  | Relate to cancer patients, cancer treatments, cancer screening/prevention, or tobacco?                              | Complete the CPRC application process.
Contact: [contact]   |  |
|  Yes
 No  | Include the use of radiation? (x-ray imaging, radiopharmaceuticals, external beam or brachytherapy)                 | Complete the AURPC Human Use Application and follow instructions on the form for submission to the AURPC committee.
Contact: [contact]  | Approval from these committees must be received prior to IRB approval; |
|  Yes
 No  | Use the Center for Magnetic Resonance Research (CMRR) as a study location?  | Complete the CMRR pre-IRB ancillary review
Contact: [contact]   |  |

## MEDICAL PROTOCOL (HRP-590)

PROTOCOL TITLE: Effect of mechanical intervention on the scalp microbiome: setting the stage for the future management of cicatricial alopecias

VERSION DATE: 05 August 2023

|  |  |   |  |
|--|--|---|--|
|  Yes
 No | Include the use of recombinant or synthetic nucleic acids, toxins, or infectious agents? | Complete the IBC application via eprotocol.umn.edu
Contact:   | These groups each have their own application process.   |
|  Yes
 No | Include the use of human fetal tissue, human embryos, or embryonic stem cells?           | Contact OBAO for submission instructions and guidance  |  |
|  Yes
 No | Include PHI or are you requesting a HIPAA waiver?  | If yes, HIPCO will conduct a review of this protocol.
Contact: [contact]  |  |
|  Yes
 No | Use data from the Information Exchange (IE)?   | The Information Exchange ancillary review will be assigned to your study by IRB staff
Contact: [contact]  | Approval must be received prior to IRB approval.  |
|  Yes
 No | Use the Biorepository and Laboratory Services to collect tissue for research?            | The BLS ancillary review will be assigned to your study by IRB staff.
Contact: [contact]  | These groups do not have a separate application process but additional information from the study team may be required. |
|  Yes
 No | Have a PI or study team member with a conflict of interest?                              | The Col ancillary review will be assigned to your study by IRB staff
Contact: [contact]   | These groups do not have a separate application process but additional information from the study team may be required. |
|  Yes
 No | Need to be registered on clinicaltrials.gov?   | If you select "No" in ETHOS, the clinicaltrials.gov ancillary review will be assigned to your study by IRB staff
Contact: [contact]   | These groups do not have a separate application process but additional information from the study team may be required. |
|  Yes
 No | Require registration in OnCore?  | If you select "No" or "I Don't Know" in ETHOS, the OnCore ancillary review will be assigned to your study by IRB staff
Contact: [contact] | Does not affect IRB approval.   |

**REVISION HISTORY**

| Revision # | Version Date | Summary of Changes   | Consent Change? |
|-------------------|---------------------|---|------------------------|
| 1                 | May 15 2022         | Change in number of treatments/duration of study   | Yes                    |
| 2                 | September 13 2022   | Addition of HairMetrix to secondary endpoint and study design   | Yes                    |
| 3                 | January 4, 2023     | Edit to HairMetrix to only occur before treatment and edited the frequency of control swabs to room air   | Yes                    |
| 4                 | March 2, 2023       | -Changed age of enrollment eligibility to 18-50 years old
- Administrative updates
-On page 11-updated sentence to indicate the treatment is over a two-week period.
-Updated the section 5.3 page 12 that participation will last approximately 2.5 weeks
-Removed the words "before treatment" on page 13 | Yes                    |
| 5                 | August 5, 2023      | -Changed total enrollment to "n=20-25", pg 10
- Updated total enrollment to state "A total of up to 25 subjects" on pg 10
-Deleted 20 males and 20 females on pg 10   | No                     |
|                   |                     |   |                        |
|                   |                     |   |                        |

## MEDICAL PROTOCOL (HRP-590)

PROTOCOL TITLE: Effect of mechanical intervention on the scalp microbiome: setting the stage for the future management of cicatricial alopecias

VERSION DATE: 05 August 2023

**MEDICAL PROTOCOL (HRP-590)**

PROTOCOL TITLE: Effect of mechanical intervention on the scalp microbiome: setting the stage for the future management of cicatricial alopecias

VERSION DATE: 05 August 2023

**ABBREVIATIONS/DEFINITIONS**

| Abbreviation | Word or Phrase      | Definition   |
|--------------|---------------------|--|
| LPP          | Lichen planopilaris | An inflammatory condition that may cause scarring hair loss. |
| AA           | Alopecia areata     | An autoimmune disease resulting in patches of hair loss.     |

## MEDICAL PROTOCOL (HRP-590)

PROTOCOL TITLE: Effect of mechanical intervention on the scalp microbiome: setting the stage for the future management of cicatricial alopecias

VERSION DATE: 05 August 2023

### 1.0 Objectives

1.1 Purpose: The objective of this study is to assess the effect of standardized scalp care, specifically mechanical cleansing with the Venus Glow™ Device and water, on the scalp microbiome. This study also seeks to characterize the microbiome of the normal, healthy scalp, thereby providing a baseline for which the scalp affected by hair and scalp disease can be compared.

### 2.0 Background

#### 2.1 Significance of Research Question/Purpose:

Perturbations in the epidermal ecosystem which interacts with the immune system have been shown to be associated with skin diseases including rosacea, folliculitis, seborrheic dermatitis/dandruff, and alopecia areata (AA). In the cicatricial alopecias such as folliculitis decalvans and lichen planopilaris (LPP), *S. aureus* is commonly isolated and treated. Why this bacteria is so commonly expressed in the cicatricial alopecias is not known. Furthermore, scalp hygiene practices, such as washing or shampooing, which may be influenced by an array of factors and are highly variable across populations, may play a role. There is little known about the effects of hygiene practices on the scalp microbiome, and much less about the microbiome of the scalp affected by cicatricial alopecias; thus, this information is needed to better understand the role of microorganisms, including *S. aureus*, in these conditions.

The development and introduction of new devices, such as the Venus Glow™, provide a unique opportunity to fill a knowledge gap and discern the effects of scalp care and treatments on scalp health and scalp flora. This study will employ the Venus Glow™ device, which is a FDA Class 1 device used for cosmetic treatments and is found mostly in medical spas and salons. It is marketed to rejuvenate skin by “cleaning pores of daily debris.” Treatment involves use of a lactic acid solution and a serum provided by the manufacturer. In this study, only water will be delivered; no serums will be added.

Through the investigational use of the Venus Glow™ device, we propose that the technique of mechanical cleansing will change the scalp microbiome composition and will result in a clinically healthier scalp.

#### 2.2 Preliminary Data:

Preliminary studies within our institution include a scalp swab assessment of participants with scarring alopecia compared to controls. The study thus far has found a predominance of *Staphylococcus*, *Propionibacterium*, and *Auritidibacter* in the frontal region of healthy control scalps. Additionally, one sample collected from a participant with dandruff had a greater proportion of *Staphylococcus* and a smaller proportion of *Propionibacterium* compared to samples, consistent with what has been reported in the literature (12,13,15,17).

## MEDICAL PROTOCOL (HRP-590)

PROTOCOL TITLE: Effect of mechanical intervention on the scalp microbiome: setting the stage for the future management of cicatricial alopecias

VERSION DATE: 05 August 2023

### 2.3 Existing Literature:

The scalp hosts a unique microbiome compared to other skin surfaces, with decreased acidity and decreased exposure to ultraviolet light. Many studies have assessed the scalp flora via swabs. The results of which are discussed below:

| Author                            | Subjects  | Methods of Analysis   | Microbe Selection Process   | Results   |
|-----------------------------------|---|---|---|---|
| Shibagaki et al.      | Healthy Japanese women-ages 21-37 (n=) v. over 60 (n=)  | Scalp Swab  | Species with ≥0.1% presence in >50% of the all subjects in at least one skin site   | Increased Proteobacteria, Klebsiella, and Prevotella in older group.  |
| Grice et al.         | Healthy humans (n=10)   | Occipital Scalp Swab  | 19 bacterial phyla were detected, but most fall within the four phyla discussed   | Propionibacterium species and Staphylococci species were the most predominant.  |
| Xu et al.            | Volunteers with varying dandruff levels (n=59)  | Scalp Swab  | 11 bacterial phyla, 123 genera, and 378 operational taxonomic units of fungi were detected  | Propionibacterium and Staphylococcus were the most predominant bacteria in both groups. Decreased Propionibacterium, increased Staphylococcus, decreased M. globosa in the dandruff group.   |
| Soares et al.        | Dandruff (n=13) v. healthy controls (n=11)  | Vertex Scalp Swab   | 274 fungal OTUs were detected, plant sequences were removed. 612 bacterial OTUs were detected, chloroplasts and mitochondria sequences were removed | Propionibacterium, Staphylococcus, and Corynebacterium were most predominant in both groups. M. restricta was the most predominant fungi in both groups. Increased Pseudomonas , Leptotrichia , Micrococcus , Selenomonas , Erwinia , Enhydrobacter , Bartonellaceae , Candida , Aspergillus , and Filobasidium in dandruff group. Decreased Propionibacterium in dandruff group.                                |
| Clavaud et al.       | Dandruff v. healthy controls  | Scalp Swab  | DNA from 3 major species was extracted.   | Propionibacterium and Staphylococci were the most predominant bacteria in both groups. M. restricta was the most predominant fungi in both groups. Decreased P. acnes , increased M. restricta , and increased S. epidermidis in dandruff group.  |
| Wang et al.          | Dandruff (n=32) v. non-dandruff controls (n=9)  | Scalp Swab  | 2,195 bacterial and 1,818 fungal sequences were detected  | P. acnes and S. epidermidis dominated both groups. M. restricta was the most predominant fungi in both groups. Increased M. restricta and Staphylococcus spp. in dandruff group. No significant difference in Propionibacterium between groups.  |
| Grimshaw et al.      | Dandruff (n=32) v. healthy controls (n=9)   | Scalp was exfoliated and resulting scale in saline was analyzed | Discussed the 8 predominant taxa from 273 fungal OTUs. Discuss the most predominant taxa from 300 OTUs  | Malassezia was the most predominant species in both groups and higher in the dandruff group. Staphylococcus and Cutibacterium were the most predominant bacteria in both groups. Non-significant decrease in Cutibacterium and increase in Staphylococcus in dandruff groups.  |
| Saxena et al.        | Dandruff (n=70) v. healthy controls (n=70)  | Vertex Scalp Swab   | Species with ≥1% abundance in ≥20 samples were analyzed   | M. globose and M. restricta were the most predominant fungi in both groups. No difference in M. restricta abundance between groups. Increased M. globose in the healthy scalp. Increased S. epidermidis in dandruff group. No difference in P. acnes abundance between groups.  |
| Park et al.          | Dandruff (n=28) and seborrheic dermatitis Korean subjects (n=29) v. Korean controls (n=45)    | Vertex Scalp Swab   | 56 bacterial OTUs that had abundance >0.05% and 39 fungi species with abundance >0.01% were analyzed  | Increased Staphylococcus sp. and M. restricta in dandruff and seborrheic dermatitis groups. Increased Propionibacterium sp. and M. globosa in control group.   |
| Lin et al.           | Dandruff (n=28) and erythema scalp Chinese Han subjects (n=29) v. Chinese Han controls (n=53) | Scalp swab from lesion and healthy sites                        | The 8 most predominant fungi and bacteria genera were discussed.  | No difference in P. acnes abundance between groups. All groups had the same predominant microbes including: Malassezia , Aspergillus , Exophiala , Aureobasidium , Phaeoacremonium , Lecanicillium , Cyberlindnera , Debaryomyces , Staphylococcus , Sediminibacterium , Corynebacterium , Pseudomonas , Phyllobacterium , Bardyrhizobium , Sphingomonas , and Bosea . |
| Juhasz et al.        | AA (n=25) v. healthy controls (n=25)  | Scalp Swap  | Not discussed.  | Decreased Firmicutes and increased Actinobacteria in AA groups.   |
| Constantinou et al.  | Frontal fibrosing alopecia (FFA) (n=6) v. lichen planopilaris (LPP) (n=6) v                   | Scalp Swap  | Five most abundant genera across samples were analyzed.   | Increased Staphylococcus in disease lesions in all alopecia participants. Increase in Staphylococcus in non-lesional sites in participants with LPP.  |

## MEDICAL PROTOCOL (HRP-590)

PROTOCOL TITLE: Effect of mechanical intervention on the scalp microbiome: setting the stage for the future management of cicatricial alopecias

VERSION DATE: 05 August 2023

|                            |   |            |                |  |
|----------------------------|---|------------|----------------|--|
|                            | alopecia areata circumscripta (AAc) (n=7) |            |                |  |
| Pinto et al.  | AA (n=15) v. healthy controls (n=15)      | Scalp Swab | Not discussed. | Increased P. acnes , decreased S. epidermidis in AA group. No difference in S. aureus abundance between groups. |

No studies have assessed the use of the Venus Glow™ device on the scalp and no studies have assessed the different scalp regions, such as the vertex, temporal and postauricular scalp, systematically.

### 3.0 Study Endpoints/Events/Outcomes

- 3.1 Primary Endpoint/Event/Outcome: The primary endpoint will be scalp swab assessment of scalp microbiome composition before and after Venus Glow™ treatment. Our hypothesis is that there will be a decrease in microbe burden on the scalp with treatment.
- 3.2 Secondary Endpoint(s)/Event(s)/Outcome(s): Secondary endpoint includes scalp swab assessment of scalp microbiome composition after participants have returned to their normal hair and scalp care routine, providing information about the normal, healthy scalp microbiome. In addition, photography comparisons with the HairMetrix device will be taken before each treatment at the swab sites for each participant.

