## 5.0 Procedures Involved

5.1 Study Design: This is a research study utilizing scalp swabs to evaluate the efficacy of the Venus Glow™ device treatment on the scalp microbiome. Healthy participants who have not been diagnosed with scalp or hair disease will be followed over a period of 2 weeks to assess their scalp microbiome and see how well the investigational device works on decreasing the microbe burden of the scalp.

*Total Enrollment (N= 20-25):* A total of up to 25 subjects between the ages of 18-50 years with different self-reported ethnicities and evaluated skin and hair types will be enrolled in the study.

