### Photo 1: Swab Sites (25)

**MEDICAL PROTOCOL (HRP-590)**

PROTOCOL TITLE: Effect of mechanical intervention on the scalp microbiome: setting the stage for the future management of cicatricial alopecias

VERSION DATE: 05 August 2023

To collect samples, sterile cotton swabs will be soaked for at least 30s in collection buffer (0.15 M NaCl, 0.1% Tween-20) and rubbed on the scalp surface in the following locations: right and left mid-frontal scalp, covering an area of 4 cm^2 per scalp section. Swabs will be stored in a collection buffer amended to a final concentration of 10% glycerol and stored at -80 °C prior to shipping/processing. If necessary, samples will be shipped to the microbiology lab on dry ice. Control swabs exposed to just room air and the buffer will be collected throughout the course of the study when treating participants. DNA will be extracted from the swab tips using the Daisy PowerSoil Pro DNA isolation kit (QIAGEN). Bacteria/archaea will be characterized by amplification and sequencing using the 515F/806R primer set targeting the V4 hypervariable region of the 16S rRNA gene. Fungal communities will be characterized by sequencing of the ITS1 region using the ITS1f/ITS2 primer set. Paired-end sequencing will be carried out at a read length of 300 bp on the Illumina MiSeq platform by the UMN Genomics Center. Bioinformatics and computational analyses of microbiome data will be done by the [name] lab using mothur software and raw data will be made publicly available on the Sequence Read Archive.

5.3 Study Duration: The total duration of participant participation will be approximately 2.5 weeks. The duration anticipated to enroll all study participants is expected to be approximately 5 months. It is anticipated that it will take just over 1 years to complete all study procedures including data analysis.

|  |   |
|--|---|

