## **15.0 Statistical Considerations**

*15.1 Data Analysis Plan:*

The primary analysis will evaluate whether there is a difference in the baseline and 2-week change in the relative abundance of pre-specified bacteria (approx. 20) between the device-treated portion of the scalp and the non-treated portion. In order to account for the within-subject correlation, mixed-effects models will be performed. As a secondary analysis, we will compare the HairMetrix images and analyze how various demographic and clinical factors such as sex and skin type impact the effect of the device.

*15.2 Power Analysis:*

Limited data are available to inform a power/sample size estimate. However, if there is a total of 38 subjects (40 initial, with 5% dropout), then we will have pre- and post-treatment data for 38 device-treated, and 38 non-treated portions of the scalp. Even when ignoring the within-subject correlation, this will allow us to have 80% power to detect an effect size of 0.7 (difference in the baseline to week 1 change between groups), assuming an alpha of 0.05.

*15.3 Data Integrity:*

- The study monitor will ensure that the investigation is conducted according to protocol design and regulatory requirements. The monitor will provide ongoing monitoring of data validity and regulatory issues (e.g., eligibility determinations, consent form process, serious adverse event reporting, IRB actions, disclosures of conflict of interest).
- Study records will be monitored at regular intervals by the study monitor. The monitor will perform source data verification and as such must be given access to the subject's primary source documentation, such as paper or electronic medical records such as consent to participate in the study, visit dates, demographic information, adverse events, concomitant medications, drug accountability, etc. that support data entries in the CRF.

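### The hypothesis of reduced microbe burden (3.1, 5.1) cannot be tested, because section 15.1 analyses only relative abundance and no total load is measured

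*Combined protocol and SAP*

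**What the plan says.** Two places in the protocol speak of burden. Section 3.1 states: "Our hypothesis is that there will be a decrease in microbe burden on the scalp with treatment". Section 5.1 says the study will "see how well the investigational device works on decreasing the microbe burden of the scalp".

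The rest of the plan speaks of composition. Section 2.1 proposes that "mechanical cleansing will change the scalp microbiome composition". The endpoint in 3.1 reads: "The primary endpoint will be scalp swab assessment of scalp microbiome composition before and after Venus Glow™ treatment".

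The laboratory work in 5.2 is DNA extraction followed by two sequencing assays. For bacteria and archaea it is "amplification and sequencing using the 515F/806R primer set targeting the V4 hypervariable region of the 16S rRNA gene". For fungi: "Fungal communities will be characterized by sequencing of the ITS1 region using the ITS1f/ITS2 primer set".

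The primary analysis in 15.1 concerns the baseline and "2-week change in the relative abundance of pre-specified bacteria (approx. 20) between the device-treated portion of the scalp and the non-treated portion". The secondary analysis there covers the HairMetrix images and how participant characteristics modify the device effect. No section plans quantitative PCR, culture or colony counts, a spike-in standard, quantification of DNA yield, or any other measure of total load.

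**The concern.** Burden is an absolute quantity, and the hypothesis gives it a direction. Relative abundance is a share of whatever was sequenced, so the total drops out. The hypothesis stated with the primary endpoint is therefore about a quantity that the plan neither measures nor analyses. The fungal part of microbe burden is further off still, because fungi are sequenced but 15.1 names no fungal outcome.

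Two misreadings become possible:

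- A fall in the share of one taxon could be reported as reduced burden although load had risen.
- If the device removed all taxa evenly, the hypothesis would be true while every true share stayed unchanged, and the result could be read as no effect on burden. Section 4.1 describes suction that removes debris, and nothing in the documents says that removal favours particular taxa.

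**Working it through.** **The plan's own figure.** The plan gives no figure for load. Its only quantitative statement is the power calculation in 15.2: 40 enrolled with 5% dropout gives 40 × 0.95 = 38 per side, with 80% power at alpha 0.05 for an effect size of 0.7, ignoring within-subject correlation. Two-sided, the detectable effect is (1.960 + 0.842) × √(2/38) = 0.64 by the normal approximation and 0.65 by the t-test, which rounds to the stated 0.7. That effect size has no unit and is not tied to a load outcome, so it does not bear on this point. More participants would not change what follows.

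**What the outcome can identify.** Let taxon *i* have count xᵢ and total load N = Σxᵢ. The analysed quantity is the share sᵢ = xᵢ/N.

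*Step 1: an even change in load leaves the shares unchanged.* If every count is multiplied by k, the share is k·xᵢ/(k·N) = sᵢ. With assumed counts 600/300/100 and k = 0.1, the counts become 60/30/10. Load falls by 90%, and the shares stay at 0.6/0.3/0.1.

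*Step 2: the same shift in shares fits opposite changes in load.* From the same 600/300/100 (total 1000):

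- Halve taxon 1: 300/300/100, total 700, load -30%, shares 0.43/0.43/0.14.
- Double taxa 2 and 3: 600/600/200, total 1400, load +40%, shares 0.43/0.43/0.14.

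*Step 3: this holds for any starting share.* Let taxon 1 start at share p, with total load set to 1.

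- Halving taxon 1: new load 1 - p/2, so the change is -p/2. Its new share is (p/2)/(1 - p/2).
- Doubling all the others: new load p + 2(1 - p) = 2 - p, so the change is +(1 - p). Its new share is p/(2 - p), which equals (p/2)/(1 - p/2).

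Any other taxon that starts at share q ends at q/(1 - p/2) in the first case and 2q/(2 - p) in the second. These are equal, so the whole composition agrees.

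| Assumed starting share of taxon 1 | Load change if it is halved | Load change if all others double | Its final share, both cases |
|---|---|---|---|
| 20% | -10% | +80% | 11% |
| 40% | -20% | +60% | 25% |
| 60% | -30% | +40% | 43% |
| 80% | -40% | +20% | 67% |

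The documents give no shares, so the counts and the 20% to 80% range are assumptions. They illustrate the ambiguity and do not predict this trial's result. The algebra holds for every p.

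**Whether another part of the plan supplies load.** The room-air and buffer control swabs in 5.2 show background DNA, not the amount on the scalp. The mothur analyses mentioned there are not specified and take the same sequence data as input. The follow-up endpoint in 3.2 is again composition. None of these gives a total.

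**The case against.** The strongest reply is that this is loose wording rather than a failed analysis. The objective in 1.1, the proposal in 2.1, both swab endpoints in section 3, the assays and the primary analysis all concern the microbiome or its composition. Burden appears in one sentence and one clause and is never defined; the authors may have meant the abundance of selected taxa. The trial still has a testable proposal, in 2.1, about the quantity that 3.1 names as its endpoint. The plan nowhere says that a change in shares will be reported as a change in burden, and the counts used above are invented.

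Most of this stands, and it limits the point. Composition can be tested with the planned data, the harm is a risk of misreading rather than a certainty, and the numbers prove ambiguity, not its size here. It does not remove the inconsistency. Section 3.1 uses both terms in adjacent sentences, only burden carries a direction, and no definition equates the two. If composition was meant, rewording is the remedy.

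A second objection concerns adding a load assay, and it also stands. By the visit table in 5.3, the right site is swabbed before and again after treatment at the same visit, while the left site is not swabbed again. A same-visit comparison of load would mix removal by the device with removal by the first swab, without an untreated control. In addition, DNA is extracted from swab tips after storage in buffer, and recovery is not described.

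**Conclusion.** The concern holds. As written, the hypothesis in 3.1 and the aim in 5.1 can be neither supported nor refuted by any result of the microbiome analysis in 15.1, because relative abundance carries no information on total load and no load is measured. Identical shares are compatible with load changes of opposite sign: -30% or +40% at an assumed starting share of 60%, and from -10% or +80% to -40% or +20% over assumed shares of 20% to 80%. Even removal of any fraction leaves every true share as it was, although observed shares could still shift through background DNA.

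The conclusion rests on reading burden as an amount, which is its natural meaning, and on the absence of any planned load measure. It does not extend to the composition endpoint or to the proposal in 2.1. This should be corrected before the results are interpreted.

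**What to change.** Restate the hypothesis in 3.1 and the aim in 5.1 as a change in community composition on the treated compared with the untreated side, in line with 2.1. Add one sentence to 15.1: no conclusion on microbial burden, in either direction, will be drawn from relative abundance.

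The cost is wording in three sections. Endpoint, comparison, visits and swabs stay the same. The burden claim is given up.

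Only if the sponsor wants to keep that claim, total bacterial and fungal load would have to be measured (16S and ITS copies per 4 cm² swab, from the DNA already extracted) and named in 3.1 and 15.1 as the outcome for it. It should then be tied to the visit-to-visit comparison of right and left sites, using the swabs taken before treatment and at the final visit, with its own analysis and power basis. No sample size can be offered, because the documents give no standard deviation or expected change for load. This option needs extra assay work for both bacteria and fungi, but no new participant procedure.
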